**Temporary COVID-19 pandemic procedures for returning to in-person visits:**

**During this time, housing sites will determine the best location for study activities, including exams/treatment, for their facility. This location may be located in areas indoors and/or outdoors at the facility.**

The number of research staff attending on-site recruitment/data collection and dental screening/treatment appointments will be kept to a minimum. Only personnel essential for completion of the appointments will attend.

Research staff will complete a screening questionnaire on a daily basis using the CWRU Daily Health Assessment (if they are reporting to campus at any time during the day) or the ADA COVID-19 Employee Screening Log (if they are reporting only to a study site) to determine work readiness. Research staff will wear appropriate PPE as determined by their work function (mask, gloves, face shields, gowns, and head covering). All research staff will wear masks at all times and will perform proper hand hygiene while on-site at the housing facilities.

**Scheduling Procedures for Recruitment, Data Collection and/or Dental Exam/Treatment appointments at the housing sites:**

- For recruitment of new participants, research staff will obtain interested individual's contact information so they may contact them by phone to explain the study and administer the COVID-19 Screening Questionnaire prior to setting up a one-on-one meeting.
- All participants will be called by a research staff member and interviewed using the COVID-19 Screening Questionnaire.
- If the COVID-19 Screening Questionnaire is NOT passed (temperature  $>100.0$ , participant experienced any of the symptoms assessed, an/or participant has tested positive for COVID-19 or been in contact with someone who has tested positive for COVID-19), the participant will NOT be scheduled at this time.
- If the COVID-19 Screening Questionnaire is passed (no temperature  $>100.0$ , no reported symptoms, and no positive COVID-19 test or contact with a positive COVID-19 patient), participants will be scheduled for an individual appointment and will be instructed to stay in their apartments on the day of the appointment until called by project staff.
- Participants will also be instructed during this call of all procedural changes which will take place on the day of their scheduled appointment.

**Appointment Day Procedures for Recruitment, Data Collection and/or Dental Exam/Treatment:**

**Prior to the appointment:**

- Research staff will call participants to be reassessed using the COVID-19 Screening Questionnaire.
- If the COVID-19 Screening Questionnaire is NOT passed (temperature  $>100.0$ , participant experienced any of the symptoms assessed, an/or participant has tested positive for COVID-19 or been in contact with someone who has tested positive for

COVID-19), the participant will NOT be seen for their appointment at this time. They may be reassessed after 14 days.

- If the COVID-19 Screening Questionnaire is passed (no temperature  $> 100.0$ , no reported symptoms assessed, and no positive COVID-19 test or contact with a positive COVID-19 patient), participants will be asked to come to the facility designated area for their individual appointment.
- If scheduled for a dental exam, participants will be asked to brush their teeth thoroughly and to use a mouth rinse if possible.
- All participants will be asked to wear a mask of their own into the facility designated meeting/exam area. If a participant does not have a mask, one will be provided to them.

At the appointment:

- Research staff will take and record participant's temperatures when they arrive for their appointment to determine if he/she may participate. If the recorded temperature is  $> 100.0$ , the participant will NOT be examined/interviewed. They may be reassessed in 14 days.
- If the participant's temperature is  $< 100.0$ , he or she may be interviewed/examined as scheduled.

Clinical Protocol for Dental Exams and Treatment:

1. Research staff will arrive at assigned site wearing face mask/covering. Staff will perform proper hand hygiene upon arrival.
2. Equipment will be set up in work areas. Once equipment is set up, it will be disinfected and appropriate barriers will be placed
  - a. Equipment includes dental chair, operator chair, compression unit, tray/light, assistant tray, sharps container, equipment supply locker
  - b. Disinfection procedure includes spraying equipment with Cavicide and allow to sit for three(3) minutes, then wipe with Caviwipes and allow to dry
3. Once research staff has taken the participant's temperature and determined that they passed the COVID-19 Screening Questionnaire, the dentist will review the health history before the participant is moved to the exam/treatment area
4. The participant will wear their mask until seated in the dental chair and the clinical team is ready to perform the dental exam. There will be no physical contact permitted, such as shaking hands, etc. Access to the treatment area should be limited to appropriate staff and the participant only, when possible.
5. Paperwork in the treatment area should be limited as much as possible, placing new paperwork away from patient contact area when possible and stored on a clipboard, under a plastic sheet protector, which may be wiped with a disinfectant wipe. Pens are not to be shared among the research staff
6. Hygienists and dentist will don proper PPE
  - a. Dentist/hygienist perform proper hand hygiene

- b. Put on disposable gown, tying all ties or snapping all snaps, this may require help from another provider
  - c. Put on surgical mask
  - d. Put on face shield
  - e. Perform proper hand hygiene again
  - f. Put on gloves, pulling down over wrists of gown
7. Participant will be seated in dental chair and will remove mask when instructed. Hygienist will place patient napkin on participant. The hygienists will perform exam while the recorder charts. The dentist will check charting, confirming areas for treatment as trained.
  - If no active decay is detected, participant will be dismissed from treatment area to complete exit paperwork with research staff.
8. The hygienists perform treatment using all necessary precautions to reduce aerosols and contamination, such as high volume evacuation and cotton rolls
  - The treatment will be SDF or ART as determined by the treatment assignment of the housing site.
9. Once treatment is complete, the dentist will check the areas of treatment
  - Photos may be taken of treatment area by research assistant
10. The hygienist will remove and dispose of the patient napkin and the participant will then don their personal mask and leave the treatment area
11. The examining hygienist and dentist will remove gloves, perform proper hand hygiene and sign necessary paperwork
  - Pens are not to be shared between staff
12. If gloves have been removed, hygienists will then perform proper hand hygiene and put on gloves. Hygienists will remove and dispose of all barriers in garbage, all instruments will be disposed of in red sharps container.
13. Hygienists will disinfect treatment area while wearing proper PPE
  - a. Spray dental chair, operator chair, compression unit, tray/light, assistant tray, sharps container, equipment supply locker with cavicide
  - b. allow to sit for three (3) minutes
  - c. wipe with Caviwipes and allow to dry
14. Hygienists will remove gloves, perform proper hand hygiene and apply new barriers as trained, to prepare for next participant. Hygienists will spray face shield with soap/water solution and wipe dry with paper towel or clean face shield with alcohol pad
15. After completing treatment for the day, equipment will be disinfected and disassembled
  - a. Spray dental chair, operator chair, compression unit, tray/light, assistant tray, sharps container, equipment supply locker with Cavicide
  - b. allow to sit for three (3) minutes
  - c. wipe with Caviwipes and allow to dry

- d. Spray and wipe floors with prepared Lysol solution and allow to dry
16. Dentist/hygienists will then remove PPE
  - a. Properly remove and discard gloves
  - b. Remove and dispose of gown
  - c. Perform hand hygiene
  - d. Remove face shield and clean with soap/water solution and a paper towel or alcohol pads
  - e. Remove surgical mask
  - f. Perform hand hygiene
  - g. All staff should don personal mask to exit the facility

\*\*\*ALL PARTICIPANTS AND PROJECT STAFF WILL BE INSTRUCTED TO CONTACT RESEARCH PERSONNEL IF THEY EXPERIENCE ANY OF THE SYMPTOMS AS ASSESSED BY THE COVID-19 SCREENING QUESTIONNAIRE/ADA COVID-19 EMPLOYEE SCREENING LOG/CWRU DAILY HEALTH ASSESSMENT, RECORD A TEMPERATURE  $>100.0$ , TEST POSITIVE FOR COVID-19 AND/OR LEARN THEY HAVE BEEN IN CONTACT WITH A PERSON WHO HAS TESTED POSITIVE FOR COVID-19 WITHIN 2 WEEKS OR 14 DAYS OF THEIR DENTAL EXAM/RECRUITMENT INTERVIEW OR WORK DAY.

Once the COVID-19 pandemic ends, we will follow the original proposed plan for all visits.

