## 7 STUDY SCHEDULE

Prior to any of the following actions, facilities will be randomized into one of two treatment intervention arms.

Refer to Appendix A for the Schedule of Events.

Temporary COVID-19 pandemic procedures:

Recruitment/Enrollment

- Study staff will receive contact information from Service Coordinators/Housing Managers for those who are interested in the study.
- Study staff will contact interested individuals by phone or video-conference and send them paper consent forms. They will review the consent form with the individual by phone or video-conference and answer any questions they may have and ensure the individual understands the study and all study procedures.
- Individuals will then be asked to sign the consent form and mail it back to the study staff in a stamped, self-addressed envelope provided to them. Study staff will sign the form and send a copy of the signed form back to the individual, along with a paper copy of the surveys.
- Study staff will then contact the individual by phone or video-conference to complete the surveys. Individuals will be asked to follow along on the paper survey while study staff reads the questions to them over the phone or video conference. Participant responses will be entered into REDCap by study staff during the phone call or video-conference.
- Exam/treatment appointments will be scheduled once the housing sites, funding agencies, IRB and CWRU have approved study personnel returning to being on-site at the housing sites.

26 and 52-week Follow-Up Data Collection

- Study staff will contact individuals due for the 26 and 52-week follow-up survey, to arrange a time to complete the survey by phone. Study staff will mail the survey to the individual prior to the survey completion phone call.
- Study staff will then contact the individual by phone at the scheduled time to complete the surveys. Individuals will be asked to follow along on the paper survey while study staff reads the questions to them over the phone. Participant responses will be entered into REDCap by study staff during the phone call.
- 26-week and 52-week exam/treatment appointments will be scheduled once the housing sites, IRB and CWRU have approved study personnel returning to being on-site at the housing sites

Once the COVID-19 pandemic ends, we will follow the original proposed plan.

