### **Baseline Dental Exam**

- Dentists will administer the Safety Questionnaire (Pre-Exam).
- Hygienists will perform initial dental exam examination at participant's respective housing facility to determine eligibility to continue in the clinical trial based on caries status.
- Study staff will record results of dental exam examination.
- Hygienists, under the direction of the study dentist, will proceed as follows:
- If the participant has an urgent cavity or another serious dental problem, they will be instructed to go for dental care immediately and their participation will end.
- If the participant has no cavities or other urgent problems, they will be instructed to continue regular visits with their dentist and their participation will end.
- If the participant has cavities that require treatment but no urgent problems, they will receive one of two treatments at this visit and will continue to participate in the research. Hygienists will administer the intervention treatment (based on study arm) to all untreated active root or coronal carious lesion with ICDAS-II lesion severity code of 3 or greater.
- If a participant reports any issue with the applied treatment within one week of the treatment date, the study team will return to the housing facility to examine and correct the treated tooth as needed. Within 48 hours, the study team will call the participant to ask the participant if the issue has been resolved and will administer a paper safety questionnaire. The completed paper safety questionnaire will be stored in the CRF folder and documentation of the return visit/treatment will be added to the participant's electronic record.

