## **7.2 26-Week Visit (T26) (Day 168 to Day 196)**

### **Dental Exam and Treatment**

- Dentists will administer the Safety Questionnaire (Pre-Exam).

- Hygienists will perform dental examination at participant's respective housing facility to evaluate caries arrest and identify new decay.
- Study staff will record results of dental examination.
- Hygienists, under the direction of the study dentist, will administer the intervention treatment (based on study arm) for all previously treated lesions and newly identified active root or coronal carious lesion with ICDAS-II lesion severity code of 3 or greater.
- Study staff will give participants referral sheets with exam results and direction to follow up with their personal dentist for routine dental care.
- If a participant reports any issue with the applied treatment within one week of the treatment date, the study team will return to the housing facility to examine and correct the treated tooth as needed. Within 48 hours, the study team will call the participant to ask the participant if the issue has been resolved and will administer a paper safety questionnaire. The completed paper safety questionnaire will be stored in the CRF folder and documentation of the return visit/treatment will be added to the participant's electronic record.

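### Step 7 of the temporary COVID-19 clinical procedure sends participants without active decay away before treatment and is not limited to baseline, which contradicts the second application due at 26 weeks

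*Combined protocol and SAP*

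**What the plan says.** The temporary block in section 7 is headed "Temporary COVID-19 pandemic procedures for returning to in-person visits". Within it, the numbered steps under Clinical Protocol for Dental Exams and Treatment run from arrival through examination and treatment to disinfection.

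- **Step 7.** The hygienist examines and a recorder charts. Then: "The dentist will check charting, confirming areas for treatment as trained". The bullet beneath reads: "If no active decay is detected, participant will be dismissed from treatment area to complete exit paperwork with research staff".
- **Step 8.** Hygienists then treat: "The treatment will be SDF or ART as determined by the treatment assignment of the housing site".
- **Reach of the block.** Section 7 says "26-week and 52-week exam/treatment appointments will be scheduled once the housing sites, IRB and CWRU have approved study personnel returning" to the sites. The temporary block closes with "Once the COVID-19 pandemic ends, we will follow the original proposed plan for all visits".

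The visit-specific text differs:

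- **Section 7.1 (baseline).** "If the participant has no cavities or other urgent problems, they will be instructed to continue regular visits with their dentist", and their participation ends.
- **Section 7.2 (26 weeks).** Hygienists, under the dentist's direction, "will administer the intervention treatment (based on study arm) for all previously treated lesions and newly identified active root or coronal carious lesion" of ICDAS-II code 3 or greater.
- **Section 6.11.** SDF is given at baseline and 26 weeks in Arm 1, and varnish at baseline and 26 weeks in Arm 2. Neither carries an active-decay condition.
- **Section 6.7.** Varnish goes on all teeth.
- **Section 8.1 and Appendix A.** Section 8.1 lists a second intervention at 26 weeks, and Appendix A marks intervention delivery at weeks 0 and 26.

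**The concern.** The trial compares twice-yearly SDF with atraumatic restorative treatment (ART) plus twice-yearly varnish. A rule that dismisses anyone without active decay makes sense at baseline, where such a person is not eligible. At 26 weeks it would act on people already enrolled, and it would select those who had responded: someone whose lesions were all arrested, with no new ones, would leave without the second application. The regimen would then depend on interim response and would no longer be the one being compared.

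The analysis would not reveal this. Section 11.4 analyses people in their randomised arm however much treatment they received. That is the right primary approach, but the effect estimates would look the same in form whether or not second applications had been skipped. Only a table of what was delivered would tell. The documents give no basis for saying which arm would be favoured.

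**Working it through.** The plan states no figure on this point, so the check compares texts.

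**Step 1: does the temporary procedure reach the 26-week visit?** Yes. Section 7 schedules 26-week exam and treatment appointments for when staff may return on site, the block governs that return, and the ordinary plan resumes for all visits only after the pandemic. Neither the heading of the numbered steps nor step 7 is restricted to baseline.

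**Step 2: does the dismissal come before treatment?** Yes. It is at step 7 and treatment is at step 8.

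**Step 3: what does each text require?**

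| Participant | Step 7 as written | Sections 6.7, 6.11, 7.1, 7.2 and Appendix A | Conflict? |
|---|---|---|---|
| Baseline, no active decay | Dismissed | Participation ends (7.1) | No |
| 26 weeks, at least one active lesion | Stays for treatment | Treated | No, as to whether the person is treated |
| 26 weeks, no active decay, Arm 1 | Dismissed | SDF, including on lesions treated before | Yes |
| 26 weeks, no active decay, Arm 2 | Dismissed | Varnish on all teeth | Yes |

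The conflict is confined to the last two rows. In Arm 2 it concerns varnish, because 6.11 gives ART at baseline only.

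**Step 4: was the dosing rule changed on purpose?** The revision history for versions 7.0 to 10.0, which introduced and adjusted the temporary procedures, describes logistics and screening and no new dosing condition. The Protocol Summary and section 4.2 treat a missed second dose at 26 weeks as a loss and raise enrolment by 40 because of it. Both point to a drafting carry-over.

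**Step 5: how many could be affected?** The number would be:

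(26-week visits held under the temporary procedure) × (share of those with no active decay) × (share of those in which the bullet was applied literally)

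The documents give none of the three factors, so no count can be computed. It may be zero.

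**The case against.** The strongest reply is that the regimen is clear elsewhere. Sections 6.7, 6.11, 7.2 and 8.1 and Appendix A agree, and one sub-bullet in a checklist that is mostly about infection control merely fails to name a visit. Section 6.11 was revised after the checklist was introduced, at versions 10.0 and 14.0, and still gives the 26-week dose without condition. Exit paperwork fits the baseline screen-out. Step 7 has the dentist confirm treatment areas as trained, and section 6.8 puts a dentist at treatment visits to see that treatment follows the protocol.

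Most of that stands. It makes the literal reading unlikely and the intended regimen plain. It does not remove the defect: the bullet is an operative instruction that says something different at 26 weeks, and the protocol does not state which text governs. Supervision to the protocol does not help where the protocol gives two rules.

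A reader might infer more, and the documents do not support it:

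- **That responders were in fact left untreated.** Nothing shows this.
- **That many people must be affected, because section 11.2 assumes 90% arrest.** That is a planning assumption for the 12-month comparison. It says nothing about week 26.
- **That the approximately 40 people without a 26-week visit measure the problem.** They are attributed to visitor restrictions and are a separate group.
- **That step 8 drops varnish.** Naming only SDF or ART is most naturally shorthand for the two arms.
- **That the same conflict arises at 52 weeks.** Sections 6.8 and 6.11 say no treatment is delivered then.

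**Conclusion.** The point holds as a minor inconsistency. Read as written, step 7 withholds the second application at 26 weeks from participants without active decay, while sections 6.7, 6.11 and 7.2 and Appendix A require it. The magnitude is unknown and may be nil.

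The conclusion rests on the text alone: the temporary procedure covers 26-week visits, the dismissal precedes treatment, and no clause limits it to baseline. It does not assume that staff followed the bullet literally; the more likely account is that a baseline rule was carried into a general checklist. It is therefore a drafting error with a possible effect on delivery, and not evidence of a deliberate change to the regimen.

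**What to change.** Make two wording changes in section 7.

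1. Begin the step 7 bullet with *At the baseline screening visit only*.
2. Add: *At 26 weeks, SDF (Arm 1, including every lesion treated before) or fluoride varnish (Arm 2, all teeth) is given whether or not active decay is detected.* The sentence should not simply point to 6.11 and 7.2 together, because they differ on ART at 26 weeks.

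Add one table. From the Intervention Delivery Tracking form (section 15.3) and the Intervention Completion Log (Table 15.4.1), report by arm the number who attended the 26-week visit but did not receive the second application. Keep them separate from the approximately 40 who missed the visit or second dose because of visitor restrictions. If the number is zero in both arms, the matter is closed.

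The cost is small, since the data are already collected. The wording helps only visits still to be held; for visits already held, only the table matters. The table may show less complete delivery of the second application than the regimen's description implies.

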### 7.1 **Baseline Visit ( $T_0$ ) (Day -30 to 14)**

#### **Recruitment/Enrollment**

Study staff will recruit potential participants at the 22 participating housing facilities in coordination with the housing service coordinators and by using an in person approach at venues scheduled at the housing facility.

- Service coordinators will be provided with an introductory letter/flyer containing study information to be given to tenants and to be posted in public areas of the facility and will arrange an informational meeting for tenants (study dentist will give a talk on the interventions as suggested by our stakeholders).
- Service coordinators will arrange in-person recruitment meetings for study staff to present information regarding the study at scheduled group events (e.g. tenant meetings, health fairs, study informational presentations). For planning purposes, service coordinators will have a sign-up sheet for those interested in the sessions. At the conclusion of the session, study staff will meet individually with those interested to:
  - Review inclusion/exclusion criteria to determine eligibility (**Refer to Sections 5.1, 5.2**) utilizing the Screening and Eligibility Form
  - Obtain informed consent by reviewing the written consent form (Refer to Section 15.3) with the potential participant; ensuring comprehension of the study and

procedures, answering any questions, signing the consent form acknowledging that informed consent was reviewed and obtaining subject signature acknowledging consent was obtained. Consent will be obtained one time prior to the initiation of any study activities and will remain in effect for the duration of the study.

